Appendix Table 2. Study Procedures Table (Open Label Rollover Extension)

Study Procedures	Post End of Blinded Treatment Visit (every 12 weeks) ^{a,e,1}	30-Day Follow-up ^k	Early Study Drugs DC ^c
Adverse Events	X	X ^f	X^{f}
Concomitant Medications	X	X	X
Complete/Symptom-Directed Physical Exam	X ^d	$X^{ m d,f}$	X f
Vital signs (blood pressure, pulse, respiration rate, and temperature) and Weight	X	X	X
Urinalysis	X	Xf	Xf
Urine Pregnancy Test ^g	X		X
Chemistry Profile ^h	X	Xf	Xf
Metabolic Assessments ⁱ	X		
Estimated Glomerular Filtration Rate	X	Xf	X
Hematology Profile ^j	X	Xf	Xf
Plasma HIV-1 RNA	X	X	X
CD4+ Cell Count and CD4%	X	X	X
Blood Storage Sample ^o	X		X
HBV Blood Panel ^m	X m		
Plasma HBV DNA	X		
HCV Serology ⁿ	X ⁿ		
HIV-1 Genotype/Phenotype ^e			Xe
Study Drug Dispensation ^b	X		
Study Drug Accountability	X		X

[figure not shown]
a Once the last participant completes the Week 96 visit and Gilead completes the Week 96 analysis, all participants will return to the clinic (within 30 days ± 6 days) for an End of Blinded Treatment Visit. At the End of Blinded Treatment Visit, if safety and efficacy of B/F/TAF FDC is demonstrated for the HIV-1 and HBV coinfected participants following review of unblinded data, participants in a country where B/F/TAF FDC is not available, will be given the option to receive B/F/TAF FDC in an open label extension phase until the product becomes accessible to participants through an access program, or until Gilead Sciences elects to discontinue the study in that country, whichever occurs first.

b Open label study drug, B/F/TAF FDC will be dispensed to participants participating in the Open-Label Rollover extension.

- Participants who discontinue study drug during the open label rollover extension portion of the study will be asked to return to the clinic within 72 hours of stopping study drugs for the Early Study Drugs Discontinuation Visit followed by a 30-Day Follow-Up Visit. The participant will not continue attending the scheduled study visits.
- d Symptom-directed physical examination as needed.
- e HIV-1 genotype and phenotype testing for participants with virologic failure. Following virologic rebound, participants will be asked to return to the clinic (2-3 weeks later) prior to the next scheduled visit or at the next scheduled study visit, for a HIV-1 RNA and HIV-1 genotype and phenotype (reverse transcriptase, protease, and integrase genotype and phenotype) blood draw. Based on the results of this testing, participants should be managed according to the Virologic Rebound Schema (Protocol Section 6.14).
- f Any adverse event or test showing abnormal results that is believed to have a possible or probable causal relationship with the study drug will be repeated weekly (or as often as deemed prudent by the Investigator) until the abnormality is resolved, returns to Day 1, or is otherwise explained.
- g Females of childbearing potential only. Positive urine pregnancy tests will be confirmed with a serum test.
- h Chemistry profile: alkaline phosphatase, AST, ALT, GGT, total bilirubin, direct and indirect bilirubin, total protein, albumin, bicarbonate, BUN, calcium, chloride, creatinine, glucose, phosphorus, magnesium, potassium, sodium, uric acid and amylase (reflex lipase testing is performed in participants with total amylase > 1.5 × ULN). At End of Blinded Treatment Visit and every 24 weeks after the End of Blinded Treatment Visit, analyses of glucose will be done as part of the fasting metabolic assessments and not as part of the chemistry profile.
- i Fasting (no food or drinks, except water, at least 8 hours prior to blood collection) glucose and lipid panel (total cholesterol, HDL, direct LDL, triglycerides) every 24 weeks. If the participant has not fasted prior to the visit, the visit may proceed, but the participant must return within 72 hours in a fasted state to draw blood for the metabolic assessments.
- j Complete blood count with differential and platelet count.
- k Participants who complete the open-label rollover extension will be required to return to the clinic 30 days after the completion of study drugs for the 30-Day Follow-Up Visit. Participants who permanently discontinue study drugs during the open-label rollover extension will be asked to return to the clinic 30 days after the completion of the Early Study Drugs Discontinuation Visit for the 30-Day Follow-Up Visit. For the purpose of scheduling a 30-Day Follow-Up Visit, a ± 6 days window may be used.
- 1 Study visits are to be completed within ± 2 days of the protocol-specified visit date based on the End of Blinded Treatment Visit date through Week 12 OL and completed within ± 6 days of the protocol-specified visit date every 12 weeks thereafter, unless otherwise specified.
- m HBV serology (HBsAg and reflex anti-HBs Ab, and HBeAg and reflex anti-HBe Ab will be performed every 48 weeks.
- n Hepatitis C virus (HCVAb) serology will be performed every 48 weeks. Participants who are HCVAb positive will have a HCV RNA test performed.
- o Plasma and serum blood storage samples will be collected for safety, virology or PK testing.

Appendix 2. Flowchart of US FDA-defined Snapshot Algorithm (for Naïve Trial)

The following flowchart for US FDA-defined snapshot algorithm is based on the US FDA Guidance on Human Immunodeficiency Virus-1 Infection: Developing Antiretroviral Drugs for Treatment {U. S. Department of Health and Human Services 2015}

^{*} On-treatment data include all data collected up to 1 day after permanent discontinuation of study drug or all available data for subjects who were still on study drug.

Appendix 3. Region Definition

Region	Country Name	Number of Participants in Safety Analysis Set (N=243)			
	China (CHN)	56			
	Hong Kong (HKG)	5			
	Japan (JPN)	7			
Asia	Korea (KOR)	2			
	Malaysia (MYS)	37			
	Thailand (THA)	94			
	Taiwan (TWN)	12			
	Dominican Republic (DOM)	10			
O/I	Spain (ESP)	7			
Other	Turkey (TUR)	9			
	United States (USA)	4			

Appendix 4. Adverse Events of COVID-19

An adverse event record will be flagged as adverse events for COVID-19 if its MedDRA PT is included in the pre-specified PT list, which includes all PTs from the narrow search of the following COVID-19 SMQs under MedDRA version 24.1 provided by Gilead PS (search name: COVID-19 (SMQ) – Narrow) and reviewed by Gilead medical monitors.

	SMQ Source
AEs for COVID-19	COVID-19 (SMQ) (Narrow Scope)

Appendix 5. Data Collection of COVID-19 Data

This appendix describes the clinical trial site collection of COVID-19 data pertaining to missed/virtual visits and the data processing algorithm that will be used to determine which visits are missing and which visits are virtual.

Data Collection

A COVID-19 supplement to the eCRF Completion Guidelines (CCG) was provided by Clinical Data Management to instruct clinical trial sites with data entry expectations pertaining to scenarios related to the COVID-19 pandemic. If a visit was missed, sites were instructed to enter "Visit missed due to COVID-19" and if an in-person visit was conducted virtually, sites were instructed to enter "Virtual visit due to COVID-19".

Determination of Missed and Virtual Visits

Natural Language Processing (NLP) will be used to search the CRF comment fields to identify instances of "COVID-19", "Virtual", or synonyms (see Table 12-1). The search terms will be maintained in a global lookup table and can be modified to tune the NLP model. Any comments with COVID-19 search terms, "Missed visit" or "Virtual visit" will be assigned as follows:

- i. If COVID-19 terms are identified through NLP and the visit date is missing, then result is "Missed Visit"
- ii. If COVID-19 and Virtual terms are identified through NLP for a visit, then result is "Virtual Visit". When there are multiple records for the same participant and the same visit, if one record could be categorized as "Virtual Visit", all records associated with this participant and this visit will be categorized as "Virtual Visit"
- iii. Otherwise result is missing

Table 12-1. Example Search Terms for "COVID-19" and "Virtual" Used to Identify Missed/Virtual Visits.

Search Terms for "COVID-19"	Search Terms for "Virtual"
COVID19	VIRTUAL
CORONA	TELEMED
CORONA VIRUS	TELEHEALTH
PANDEMIC	TELEPHONE
OUTBREAK	REMOTE
CRISIS	TELEMEDICINE
LOCKDOWN	TELECONSULTATION
QUARANTINE	TELEPHONICALLY
SHELTER	PHONE
	HOME VISIT
	ZOOM
	SKYPE

Appendix 6. Hepatic Events

An adverse event record will be flagged as a hepatic event if its MedDRA PT is included in the pre-specified PT list, which includes all PTs from the broad search of the following 15 SMQs under MedDRA version 25.1 provided by Gilead PS (search name: Non-infectious, non-congenital hepatobiliary disorders) and reviewed by Gilead medical monitors.

	SMQ Source				
	Biliary neoplasms benign (incl cysts and polyps) (SMQ)				
	Biliary malignant tumours (SMQ)				
	Biliary tumours of unspecified malignancy (SMQ)				
	Biliary system related investigations, signs and symptoms (SMQ)				
	Biliary tract disorders (SMQ)				
	Gallbladder related disorders (SMQ)				
	Gallstone related disorders (SMQ)				
Hepatic Events (HEP)	Cholestasis and jaundice of hepatic origin (SMQ)				
	Hepatic failure, fibrosis and cirrhosis and other liver damage-related conditions (SMQ)				
	Hepatitis, non-infectious (SMQ)				
	Liver neoplasms, benign (incl cysts and polyps) (SMQ)				
	Liver malignant tumours (SMQ)				
	Liver tumours of unspecified malignancy (SMQ)				
	Liver related investigations, signs and symptoms (SMQ)				
	Liver-related coagulation and bleeding disturbances (SMQ)				

Appendix 7. Programming Specification

- 1. AGE calculated as follows:
 - a) AGE (years) is calculated from the number of days between the date of birth (DOB) and Day 1 (first dose date),
 - b) Use the SAS INTCK function to determine the number of "1st-of-month days" (eg, January 1st, February 1st, March 1st) between DOB and Day 1 (inclusive),
 - c) Divide the result in (b) by 12,
 - d) AGE = the integer of the result in (c),
 - e) If the DOB and Day 1 have the month in common and the birthday is later in the month than the date of Study Day 1, then subtract one from the AGE result above.

For participants randomized and never dosed with study drug, age will be calculated from the date of randomization.

- 2. All screened participants refer to all participants who are screened (ie, with nonmissing screening date) and have a screening number. For summaries, the same participant is counted only once. DOB and other demographic information such as sex, race, ethnicity, country, and initials will be used to identify unique screened participants.
- 3. Screen failure participants are the participants who are screened and answered "No" for any inclusion criteria or "Yes" for any exclusion criteria regardless of which version of protocol the participant was consent to.
- 4. Participants in the randomized analysis set are defined as participants randomized into the study. IXRSRAND is the source to determine whether the participant is randomized (ie, participant with nonmissing RGMNDTN in the IXRSRAND dataset) and confirmed by the eCRF ENROLL dataset (ie, ENROLLYN = "Yes" in ENROLL dataset).
- 5. Randomized treatment (ie, TRT01P in ADSL) are derived from IXRSRAND, while actual treatment received (ie, TRT01A in ADSL) is assigned as the randomized treatment if participant took at least 1 dose of study drug and assigned as blank if participant never dosed.
- 6. Enrollment by Stratum: using actual HBeAg, HBV DNA and CD4+ cell count screening value, the last screening value (with visitnum < 0) prior to randomization date and time.
- 7. In disposition table, the reasons for premature discontinuation are displayed in the order as they appear on the eCRF.
- 8. For the definition of Full Analysis Set regarding (3) have at least 1 post baseline HIV-1 RNA or HBV DNA results while on study drug: on study drug means the same as on-treatment (ie, postbaseline data up to 1 day after permanent discontinuation of study drug or all available postbaseline data for participants who were still on study drug).

9. Body mass index (BMI)

BMI will be calculated as follows:

• BMI = (weight [kg])/ (height [meters]2)

Baseline height and weights measured at each visit will be used for this calculation.

- 10. Please note, "Not Permitted", "Unknown", or missing categories will be excluded for percentage calculation. For Mode of infection (HIV and HBV Risk Factors), where "Unknown" will be included for percentage calculation, since a participant may fit more than 1 HIV risk factors, percentage may add to more than 100%.
- 11. Last Dose Date and Last Study Date
 - a) Last Dose Date (ie, TR01EDT or TR01EDTC for randomized phase last dose date, and TR02EDT or TR02EDTC for extension phase last dose date) in ADSL was defined in Section 3.8.1.

Randomized Phase Last Dose Date:

For B/F/TAF or DTG + F/TDF subjects with a partial last dosing date (ie, month and year of last dose are known), the minimum of {(extension phase first dose date – 1 day, if available), (the latest of the dispensing dates of study drug bottles, study drug start dates and end dates (based on EX dataset with study drug in randomized phase), and the imputed last dose date [day imputed as 15])} will be used as the final imputed last dose date. However, if dispensing date's month is after last dose date's month, data query is needed. If subject died and the death date is complete (ie, not partial date) and before the imputed last dose date, the complete death date should be used as the imputed last dose date.

Extension Phase Last Dose Date:

For subjects with a partial last dosing date (ie, month and year of last dose are known), the minimum of { (the latest of the dispensing dates of study drug bottles, study drug start dates and end dates (based on EX dataset with study drug in extension phase), and the imputed last dose date [day imputed as 15])} will be used as the final imputed last dose date. However, if dispensing date's month is after last dose date's month, data query is needed. If subject died and the death date is complete (ie, not partial date) and before the imputed last study date, the complete death date should be used as the imputed last study date.

b) Last Study Date is the latest of the randomized or extension phase (if available) study drug start dates and end dates, the clinic visit dates, and the laboratory visit dates, including the 30-day follow-up visit date. If study drug start dates or end date is partially missing (ie, only year and month are known), the day will be imputed as 15 for the purpose of this analysis.

If participant died and the death date is complete (ie, not partial date) and before the imputed last study date, the complete death date should be used as the imputed last study date.

12. Toxicity Grades:

Two type of treatment emergent lab abnormalities flag variables will be derived for laboratory data as applicable. For treatment emergent flag used in listing for randomized analysis set, the baseline toxicity grade will be based on baseline value defined as the last nonmissing value obtained on or prior to the first dose of randomized study drug. For treatment emergent flag used for the All B/F/TAF analysis summary and listing using all B/F/TAF analysis set, the baseline toxicity grade will be based on baseline value defined as the last nonmissing value obtained on or prior to the first dose of B/F/TAF.

Treatment-emergent laboratory abnormalities will be summarized for all B/F/TAF analysis, following the same rule bellows.

- a) For toxicity grade summaries, include all postbaseline graded results up to 30 days after the last dose of study drug B/F/TAF, not just those used in by-visit summaries.
- b) For glucose grading, as specified in this program specification Section 7.2, the treatment-emergent flag cannot be determined for nonfasting glucose (including glucose results without a known fasting status). As a result, these records will be excluded from the "Maximum Treatment-emergent Toxicity Grade" summary in the "Treatment-emergent Laboratory Abnormalities" or "Treatment-emergent Grade 3 or 4 Laboratory Abnormalities" summary tables. In addition, fasting glucose and non-fasting glucose will be listed as two separate laboratory tests in the "Laboratory Abnormalities" and "Grade 3 or 4 Laboratory Abnormalities" listings. Only a maximum postbaseline toxicity flag will be displayed and the treatment-emergent flag will not be displayed for nonfasting glucose as the treatment-emergent flag cannot be determined for nonfasting glucose.

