8.2.1.3. Safety

The primary analysis set for safety analyses is defined as safety analysis set, which will include all subjects who (1) are randomized into the study and (2) have received at least 1 dose of study drug. All the data collected up to 30 days after subjects permanently discontinue their study drug will be included in the safety summaries, unless specified otherwise. Subjects will be grouped according to the treatment they actually received.

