Note that all data for participants who actually receive DTG + F/TDF in the randomized phase and do not receive any dose of B/F/TAF in the extension phase will be excluded from all B/F/TAF analysis. The actual treatment received will differ from the randomized treatment only when the actual treatment received differs from randomized treatment for the entire treatment duration.

Analysis results will be presented using descriptive statistics. For categorical variables, the number and percentage of participants in each category will be presented; for continuous variables, the number of participants (n), mean, standard deviation (SD) or standard error (SE), median, first quartile (Q1), third quartile (Q3), minimum, and maximum will be presented.

For the All B/F/TAF analysis, no statistical comparison between treatment groups will be conducted.

By-participant listings will be presented for all participants in the all randomized analysis set unless otherwise specified, and sorted by participant ID number, visit date, and time (if applicable). Data collected on log forms, such as AEs, will be presented in chronological order within a participant. The treatment group to which participants were randomized will be used in the listings. Most listings will be provided for the all randomized analysis set for data from both phases of the study. Some listings for the all B/F/TAF safety analysis set will also be provided.

In general, age (in years) on the date of the first dose of study drug will be used for analyses and presentation in listings. For randomized but never dosed participants, age on the date of randomization will be used. For screen failures, age on the date of the informed consent was signed will be used. If only birth year is collected on the eCRF, "01 January" will be used for the unknown birth day and month for the purpose of age calculation, similarly, if only birth year and month are collected on the eCRF, "01" will be used for the unknown birth day for the purpose of age calculation.

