3.2. Participant Grouping

For analysis using the All Randomized Analysis Set, participants will be grouped by the randomized treatment (labeled as B/F/TAF vs. DTG + F/TDF).

For all analyses included in the all B/F/TAF analysis, participants will be grouped into the following 2 groups:

- B/F/TAF group: This group includes all participants who actually received B/F/TAF in the randomized phase of this study, regardless whether participants receive any B/F/TAF in the extension phase or not.
- DTG + F/TDF to B/F/TAF group: This group includes all participants who actually received DTG + F/TDF regimen in the randomized phase of this study and then receive at least 1 dose of B/F/TAF in the extension phase.

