4.3. Protocol Deviations

A listing will be provided for all randomized participants who violated at least 1 inclusion or exclusion criterion. The listing will include the criteria not met. A listing of participants who received the wrong study drug will also be provided.

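### The SAP's programming rule for actual treatment omits the wrong-drug-throughout exception in SAP Section 3, so the two rules conflict for any such participant

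*SAP*

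**What the plan says.** The protocol sets the grouping rule for safety in Section 8.2.1.3: "Subjects will be grouped according to the treatment they actually received". SAP Section 7.8 declares no departure from the protocol's safety analyses.

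The SAP body applies the same principle to the final analysis. Section 3 allows actual treatment to depart from randomised treatment "only when the actual treatment received differs from randomized treatment for the entire treatment duration". Section 3.2 defines the B/F/TAF group as treated: "This group includes all participants who actually received B/F/TAF in the randomized phase of this study". The switch group (DTG + F/TDF, then B/F/TAF in the extension) is defined in the same way, and Section 3.8.1 makes Study Day 1 depend on which regimen was actually received.

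The programming specification (Appendix 7, item 5) reads differently. "Randomized treatment (ie, TRT01P in ADSL) are derived from IXRSRAND", that is, from the randomisation system. Actual treatment, TRT01A, "is assigned as the randomized treatment if participant took at least 1 dose of study drug", and is "assigned as blank if participant never dosed". No other item in Appendix 7 modifies this or derives TRT01A from dispensing or dosing records.

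Section 4.3 provides for wrong-drug cases to be reported: "A listing of participants who received the wrong study drug will also be provided".

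**The concern.** An as-treated variable exists to record the participants whose regimen was not the one they were assigned. Item 5 fills it from the assignment, so among dosed participants TRT01A equals TRT01P by construction and the exception in Section 3 cannot arise from it. A programmer working from Appendix 7 and a reader working from Section 3 would place the same participant in different groups.

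At stake is the content of the final All B/F/TAF summaries, which are meant to describe experience on B/F/TAF. If their groups come from TRT01A, a wrong-regimen participant could bring comparator data into them, or have genuine B/F/TAF data omitted or counted from the wrong starting point.

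**Working it through.** The plan gives no figure to reproduce. The check is to put the two rules side by side for each possible participant. I read the entire treatment duration as the whole randomised phase, because only one regimen is given in the extension.

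| Participant | Actual treatment under SAP Section 3 | TRT01A under Appendix 7, item 5 | Agree? |
|---|---|---|---|
| A. Correct drug throughout | Randomised arm | Randomised arm | Yes |
| B. Wrong drug for part of treatment | Randomised arm | Randomised arm | Yes |
| C1. Randomised to B/F/TAF, took DTG + F/TDF throughout | DTG + F/TDF | B/F/TAF | **No** |
| C2. Randomised to DTG + F/TDF, took B/F/TAF throughout | B/F/TAF | DTG + F/TDF | **No** |
| D. Never dosed | In no as-treated group | Blank | No conflict |

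The consequences in rows C1 and C2 hold if the groups in Section 3.2 are built from TRT01A.

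- **C1.** Section 3 excludes this person's randomised-phase data from the All B/F/TAF analysis. The person enters only through extension dosing, in the switch group. Under item 5 the person sits in the B/F/TAF group from the first randomised dose, so comparator data are summarised as B/F/TAF data.
- **C2.** Section 3.2 puts this person in the B/F/TAF group from the first randomised dose. Under item 5 the person is left out if there was no extension dosing. With extension dosing, the person is in the switch group, and Study Day 1 and baseline are set at extension entry. Protocol 6.6.2 bars anyone who stopped study drug before the End of Blinded Treatment Visit from the extension, and blinded treatment lasts at least 96 weeks. The shift is therefore at least 96 × 7 = 672 days.

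**Size per case.** The number of C1 and C2 participants is not given, so I show one case as a scale only.

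- Against the safety set of 243 (SAP Appendix 3): 1/243 = 0.41%, about 0.4%.
- Against one planned arm of 120: 1/120 = 0.83%.
- Against the switch group: not calculable, because its size is not stated.
- With no such participant: zero.

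**Reach.** SAP Section 3 bases the tables of the final analysis on the All B/F/TAF data, without comparison between groups. By-participant listings and summaries of all randomised participants use the randomised arm (Sections 3 and 3.2), so item 5 does not alter their grouping. SAP Section 6 states that the primary and secondary analyses at Weeks 48 and 96 are already done and will not be repeated. The protocol's full analysis set (Section 8.2.1.2.1) groups by randomised treatment in any case.

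**The case against.** The strongest reply is that item 5 is shorthand for the usual case and that the SAP body governs. TRT01A is named nowhere else, and no section says that a table, set or group is built from it. Sections 3.1.2 and 3.1.3 define the All B/F/TAF sets by receipt of a B/F/TAF dose. Section 3.8.1 takes Study Day 1 from the study drug administration form. The code may therefore work from dosing data and be correct whatever item 5 says. A swap lasting the whole phase is also unlikely: under Protocol 5.1 the randomisation system assigns bottle numbers at each visit, so it would take repeated misallocation or a very short exposure. No document reports a case.

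Much of this stands, and it rules out several stronger conclusions that a reader might draw:

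- *That participants are misclassified throughout the All B/F/TAF tables.* This presumes both that a whole-phase swap occurred and that the tables use TRT01A. The documents establish neither.
- *That the plan cannot detect a wrong-drug error.* Section 4.3 lists such participants independently of TRT01A. What is missing is a route from that listing to the variable.
- *That item 5 could label a participant randomised to control as exposed to B/F/TAF.* It cannot, because that person keeps the control label. False exposure arises only in C1; in C2 the error is omission or a late start.

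The contradiction itself remains. Nothing in the SAP says that the body overrides the programming specification, and item 5 gives the wrong answer in the only situation for which an as-treated variable is needed.

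**Conclusion.** The point holds as a contradiction within the SAP, and it is minor. As written, item 5 cannot produce the exception in Section 3, and it conflicts with the as-treated grouping in SAP Section 3.2 and Protocol 8.2.1.3. The rules disagree only for a participant on the wrong regimen for the whole randomised phase.

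Any effect on results requires at least one such participant and groups programmed from TRT01A; the documents settle neither. With no such participant the effect is nil. Each one would be about 0.4% of the safety set, or about 0.8% of a planned arm. Only descriptive final summaries are exposed. A reader might suspect that the non-inferiority conclusions are affected, but this SAP does not carry out those comparisons, and the earlier SAPs that did are not among the documents.

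**What to change.** Amend Appendix 7, item 5 so that TRT01A is taken from the dispensed-kit and study drug administration records when the regimen received differed from the randomised one for the entire duration, and equals TRT01P otherwise (blank if never dosed, as now). Add a check of TRT01A against the wrong-study-drug listing in Section 4.3, and state whether the groups in Section 3.2 are built from TRT01A or from dosing data.

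This costs one line of specification and a short check of existing records. If the outputs are already final, a sentence in the clinical study report is enough where no participant took the wrong regimen throughout. SAP Section 1 already sends later changes to that report. If there was such a participant, the affected All B/F/TAF summaries should be rerun.

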4.2. Extent of Study Drug Exposure and Adherence

4.2.1. **Duration of Exposure to Study Drug**

Duration of exposure to study drug will be defined for the all B/F/TAF analysis. For the all B/F/TAF analysis, the terms "first dose date" and "last dose date" in the text below refer to the first dose date and last dose date defined for the all B/F/TAF phase analysis. Duration of exposure to study drug will be defined as (the last dose date – the first dose date + 1), regardless of temporary interruptions in study drug administration, and will be expressed in weeks using up to 1 decimal place (eg, 4.5 weeks).

Duration of exposure to study drug will be summarized using descriptive statistics (sample size, mean, SD, median, Q1, Q3, minimum, and maximum) and as the number and percentage of participants exposed for specified periods, eg, \geq 4 weeks (28 days), \geq 8 weeks (56 days), \geq 12 weeks (84 days), \geq 24 weeks (168 days), \geq 36 weeks (252 days), \geq 48 weeks (336 days), \geq 60 weeks (420 days), \geq 72 weeks (504 days), \geq 84 weeks (588 days), \geq 96 weeks (672 days), \geq 108 weeks (756 days), \geq 120 weeks (840 days), \geq 132 weeks (924 days), \geq 144 weeks (1008 days), etc.

Summaries will be provided by treatment group for participants in All B/F/TAF Analysis Set for the all B/F/TAF analysis, respectively. No inferential statistics will be provided.

Time to premature discontinuation of study drug will be analyzed by treatment group using the Kaplan-Meier (KM) method for the All B/F/TAF Analysis Set. No statistical comparisons will be made for the all B/F/TAF analysis. A plot of KM estimates for the time to premature discontinuation of study drug by treatment group will be generated for the All B/F/TAF analysis. Participants who completed study drug will be censored at the last dose data of the study.

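### The SAP's extension-phase last-dose rule caps the wrong date at death, so an imputed last B/F/TAF dose can fall 1 to 14 days after the participant died

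*SAP*

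**What the plan says.** Item 11 a) of SAP Appendix 7 (Programming Specification) has two parallel paragraphs, one for the randomized-phase last dose date and one for the extension-phase last dose date.

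- **Extension phase, when it applies:** "For subjects with a partial last dosing date (ie, month and year of last dose are known".
- **Extension phase, value:** the latest of the bottle dispensing dates, the study drug start and end dates, "and the imputed last dose date [day imputed as 15])} will be used as the final imputed last dose date".
- **Extension phase, death rule:** "If subject died and the death date is complete (ie, not partial date) and before the imputed last study date", with the consequence "and before the imputed last study date, the complete death date should be used as the imputed last study date".
- **Randomized phase, death rule:** the same construction, but "and before the imputed last dose date, the complete death date should be used as the imputed last dose date".

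Item 11 b) then defines the last study date as a separate variable with its own death rule, which begins "If participant died and the death date is complete (ie, not partial date) and before the imputed last study date".

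SAP Section 3.8.1 defines the last dose date for the All B/F/TAF analysis from B/F/TAF end dates across both phases and contains no death rule. SAP Section 4.2.1 computes exposure as last dose date minus first dose date plus 1. It also says: "Time to premature discontinuation of study drug will be analyzed by treatment group using the Kaplan-Meier (KM) method".

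**The concern.** The death sentence sits under a heading about the last dose date and follows a last-dose imputation, yet it acts on a different variable. It repeats what item 11 b) already does and leaves the last dose date unbounded by death. The same data pattern is therefore handled correctly in the randomized phase and incorrectly in the extension.

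This final analysis bases its table summaries on All B/F/TAF data, with randomized-phase data kept for listings (SAP Section 3). The uncapped rule is therefore the one closer to the reported exposure summaries. At stake is a derived date that cannot be true: a dose after death, and after the last study date that item 11 b) has cut back to death.

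**Working it through.** The plan gives no figure to reproduce here. The check sets the two rules side by side and then works through the dates.

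**Step 1. Which date each death rule changes**

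| SAP Appendix 7 | Date being derived | Date capped at death |
|---|---|---|
| Item 11 a), randomized phase | Last dose date | Last dose date |
| Item 11 a), extension phase | Last dose date | Last study date |
| Item 11 b) | Last study date | Last study date |

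Capping the last study date does not feed back into the extension last dose date.

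**Step 2. Whether anything else bounds the date**

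- Section 3.8.1 has no death rule. Its rule for missing All B/F/TAF last dose dates gives as examples a date with only the year known or a date wholly missing.
- The data query in the extension paragraph fires when a dispensing month is later than the last-dose month. It does not detect a death on days 1 to 14 of the last-dose month.
- The paragraph asks for a minimum but lists one term, so the minimum returns that term unchanged.

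**Step 3. Size**

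Let death fall on day d of the known last-dose month, with no dispensing, start or end date recorded after death.

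- Imputed last dose = the later of (latest recorded drug date, day 15).
- For d = 1 to 14, every recorded drug date is before day 15, so the imputed date is day 15.
- Days after death = 15 - d.

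| Day of death | Extension rule as written | With the randomized-phase death rule |
|---|---|---|
| 1 | 15 - 1 = 14 days after death | 0 |
| 3 | 15 - 3 = 12 | 0 |
| 7 | 15 - 7 = 8 | 0 |
| 14 | 15 - 14 = 1 | 0 |
| 15 or later | 0 | 0 |

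An enumeration of every death day in every month of 2022 to 2024, with the latest recorded drug date 0 to 99 days before death, gave the same result: a maximum of 14 days as written. If the last-dose month is earlier than the death month, day 15 of the earlier month precedes death and no error arises.

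The values 1 to 14 sum to 105. The mean is 105/14 = 7.5 days if death is equally likely on days 1 to 14, or 105/30 = 3.5 days over all days of a 30-day month.

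**Worked example.** The last dose is in March with the day unknown, the last bottle was dispensed in January, and death is on 3 March. The randomized-phase death rule gives 3 March. The extension rule gives 15 March, 12 days after death.

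**Step 4. What moves downstream**

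- *Exposure* (Section 4.2.1): too long by 15 - d days, at most 14/7 = 2.0 weeks, wherever the imputed extension date serves as the All B/F/TAF last dose date.
- *Treatment-emergent death* (Section 7.1.6): the window runs from first dose to last dose plus 30 days. The death lies inside it with or without the cap, so the classification does not change.
- *Primary and secondary endpoints*: analyzed at Weeks 48 and 96 and not repeated (Section 6), so unaffected.

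**The case against.** The best reply is that this is a copying slip whose intent is plain. The heading, the preceding imputation and the adjacent paragraph all point to the last dose date, and a programmer reading both paragraphs might correct it unprompted. That is fair as to cause, and nothing suggests the sponsor chose this rule. But a programming specification is meant to be followed literally, and followed literally it gives an impossible date.

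Two further objections limit the consequences, and both stand.

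- A reader might infer that the imputed extension date is always the All B/F/TAF last dose date for anyone treated in the extension. Section 3.8.1 makes that a reasonable inference, because it takes the latest B/F/TAF end date over both phases. However, only its randomized-phase text refers other partial dates to the programming specification; the All B/F/TAF text does not.
- A reader might infer that Kaplan-Meier discontinuation times will run past death. Section 4.2.1 states a censoring time for participants who completed study drug, but not the event time for those who discontinued early. The effect is possible, not established.

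The one-term minimum is not a second error. The other term in the randomized-phase paragraph, the day before the first extension dose, has no counterpart in the extension.

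The reach is also narrow. Extension entry is restricted to countries where B/F/TAF is not available, and several conditions must coincide.

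**Conclusion.** Wrong as written, and minor. The extension-phase paragraph leaves the imputed last dose date without a death cap and duplicates item 11 b).

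An error of 15 - d days (1 to 14) arises only when all of these hold:

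- the day of the last extension dose is unknown but its month and year are known;
- the death date is complete;
- death falls on days 1 to 14 of that same month;
- no later dispensing, start or end date is recorded.

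Exposure duration would then be overstated by that amount, given that the imputed date is carried into the All B/F/TAF analysis. Time to premature discontinuation may be overstated too. These summaries are descriptive, with no comparison between groups.

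A reader might conclude that a participant in this trial has been given a dose date after death. The documents do not show that anyone meets the conditions; they show only that the rule permits it.

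**What to change.** In the Extension Phase Last Dose Date paragraph of SAP Appendix 7, item 11 a), replace *last study date* with *last dose date* in both places, to match the randomized-phase paragraph. With that change the imputed dose cannot fall after a complete death date. No extra term is needed in the minimum, since it would cap the same date twice.

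The cost is two words. SAP Section 1 requires changes made after finalization to be documented in the CSR, so if the SAP is already final, add a line there.
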